6.7.5 Secondary Objectives and Endpoints

The secondary endpoints will also be assessed descriptively with frequencies and percentages. Confidence intervals for proportions will not be calculated where appraisals cannot be dichotomized to a correct or incorrect answer.

All HCPs, whether or not they have read, or recall having read the DHCP letter, will be asked a multiple choice question about the source of information (e.g. professional knowledge) or approach (e.g. guessing) that best characterized their response to the key safety questions.

Reactions to the DHCP letter based on the degree of agreement or disagreement with statements about the information will be responded to only by those HCPs affirming that they have read the DHCP letter. Specifically, statements to be evaluated include:

- The discussion of prescribing information encouraged me to better counsel my patients about the use of Humulin[®] R U-500 KwikPen[®].
- I found the description of product features to be useful.

- I learned better how to respond to possible adverse events as a result of reading this communication.
- I found the summary of important safety information to be a useful extension of product labeling.

Planned behavior will be addressed by two questions. The first queries the HCP's understanding about the need for patient counselling with Humulin® R U-500 KwikPen® while the second directly asks the HCP about their intention to counsel patients.

6.8 Quality Control

User Acceptance Testing (UAT) will be performed on the survey using a sample of 8-10 HCPs. The UAT procedure is designed to assess comprehension among HCPs regarding the words and phrases used in select survey questions and response options. UAT will also assess the clarity of the survey questions as presented to HCPs and the interest and acceptance of the surveys among all prospective HCPs and flow and ease of completing the surveys.

Online administration allows for additional randomization of response options, offsetting potential order effects. Questions pertaining to reading and reactions to the DHCP letter are asked after the risk questions. During the course of online administration, the back-button on the survey is disabled preventing alteration of responses once reviewed and entered.

The data are also checked as part of the UAT process to make sure that all of the data collected within the online survey environment are correctly extracted from the system for use in the programming environment.

In addition to the UAT processes for the survey instrument and programming environment, several other strategies will be used to ensure data quality. The randomized sampling strategy outlined above helps ensure representativeness, avoid volunteer bias, and provides an additional means for ensuring valid data. In the analysis, demographic criteria are summarized for those who met survey inclusion criteria against those who did not meet the criteria.

All statistical programs will be developed and validated using good programming practice guidelines. This is a one-time cross-sectional survey with HCPs, there is no risk to any patients, and Institutional Review Board (IRB) approval is not required.

All analyses will be performed using SAS® Version 9 (or later) software. Covance will follow Covance's standard operating procedures in the creation and quality control of all tables, listings, figures and analyses. Lilly or its designee will review all tables, listings, and figures for accuracy.

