6.10 Measures to Minimize Bias

HCPs completing the screener and meeting the Humulin[®] R U-500 KwikPen[®] survey eligibility requirements will be directed to participate in the online survey. Survey biases will be minimized through carefully constructed, non-leading survey questions, and a thorough internal validation process. Online forms will be programmed such that HCPs have access to only one survey question at a time; once a question is submitted, HCPs do not have the option of revisiting it, i.e., the back button is disabled. Lists of response options will be randomized to minimize the potential for positional bias.

Correct responses will be provided to the physicians following recording of their response, allowing for feedback on performance and reinforcing correct information and/or best clinical practice.

7 Protection of Human Subjects

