15. Please answer True, False, or I don't know for each of the following statements regarding Humulin® R U-500 KwikPen®.

		True	False	I don't know
a	It is appropriate to prescribe Humulin® R U-500 KwikPen® to	0	0	0
	patients needing more than 200 units of insulin per day.	1	2	3
b	It is important to clearly specify the units of insulin (5-unit	0	0	0
	increments) on the prescription when prescribing Humulin® R U-	1	2	3
	500 KwikPen [®] .			
c	When prescribing Humulin [®] R U-500 KwikPen [®] it is important to	0	0	0
	inform patients of their dose in units of insulin.	1	2	3
d	When administering the Humulin [®] R U-500 KwikPen [®] , patients do	0	0	0
	not need to convert the dose since the dose window shows the	1	2	3
	number of units to be injected.			
e	It is important to instruct your patients that they should always have	0	0	0
	a backup Humulin [®] R U-500 KwikPen [®] available.	1	2	3
f	It is important to instruct your patients not to count clicks to	0	0	0
	determine their dose.	1	2	3

[PROGRAMMING NOTE: Randomize the list above a-f.]

16. In the event of a Humulin® R U-500 KwikPen® malfunction, what would you instruct patients to do? (please select all that apply)

□ Use a backup pen
□ Use a syringe to withdraw the insulin from the KwikPen®
□ Contact a pharmacist or healthcare professional
□ Contact the Lilly Answer Center for more information at [name]

17. My answers to the true/false statements earlier about the Humulin® R U-500 KwikPen® were based on...(choose all that apply)

□ Professional knowledge about the use of human insulin products.
□ Previous experience with KwikPen® technology in other Lilly products such as Humalog □ Familiarity with the Humulin® R U-500 KwikPen® package insert.
□ Knowledge gained from interaction with Lilly's sale representative.
□ Knowledge gained from the Humulin Dear Health Care Provider letter.

[PROGRAMMING NOTE: Randomize the response options above 1-7.]

Study Protocol for Humulin® R U-500 KwikPen®

₆ □ Guessing

7 □ Online information

labeling.

18. Did you read the Dear Health Care Provider letter provided to you by Eli Lilly and Company on "Important Prescribing Information" for the Humulin® R U-500 KwikPen® (insulin human)?
₁ □ Yes
₂ □ No
3 □ I don't recall
[PROGRAMMING NOTE: If participant answers "1" then go to following items based on
agreement scales. If participant answers "2" or "3" skip the following series of 4 items identified under 19 and go to the following question.]

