19. Based on your reading of the Dear Health Care Provider letter provided to you by Lilly, please evaluate your reaction to the material you received by indicating the level of your agreement or disagreement with the following statements:
a. The discussion of prescribing information encouraged me to better counsel my patients about the use of Humulin® R U-500 KwikPen®.
1 ☐ Strongly disagree
2 □ Disagree
3 □ Neutral
₄ □ Agree
5 □ Strongly Agree
b. I found the description of product features to be useful.
¹ ☐ Strongly disagree
2 □ Disagree
3 □ Neutral
₄ □ Agree
5 □ Strongly Agree
c. I learned better how to respond to possible adverse events as a result of reading this
communication.
1 ☐ Strongly disagree
2 □ Disagree
3 □ Neutral
₄ □ Agree
5 □ Strongly Agree
d. I found the summary of important safety information to be a useful extension of product

₁ ☐ Strongly disagree
2 □ Disagree
3 □ Neutral
₄ □ Agree
5 □ Strongly Agree
20. Do you or another healthcare professional at your practice discuss the safe use of the Humulin® R U-500 KwikPen® with patients receiving their initial prescription?
☐ Yes, I directly counsel my patients.
Patient counseling about the use of medicines or new products is the responsibility of a nurse or diabetes educator in my practice setting.
No, counseling is generally not provided for patients about the use of prescription insulin.
15 100, counseling is generally not provided for patients about the use of prescription insulin.
21. Given what you know about Humulin [®] R U-500 KwikPen [®] , mark the best answer:
☐ The product's ease of use and advanced safety features make counseling by prescribers unnecessary.
☐ Prescribers should counsel their patients about the safe use of this product.
Any potential medication error is likely to result from dispensing and counseling is best left to pharmacists in their interactions with patients.
Humulin [®] R U-500 KwikPen [®] is not fundamentally different from any other human insulin
product and patients with experience in self-administration can use the product safely based on product instructions.
22. Based on my knowledge about Humulin [®] R U-500 KwikPen [®] , I intend to counsel patients on its use.
₁ □ Yes
2 □ No

[PROGRAMMING NOTE: End of Survey Questions]

Study Protocol for Humulin® R U-500 KwikPen®

Closing

[PROGRAMMING NOTE: Display the following when complete or screen failed]

[PROGRAMMING NOTE: Ask respondent for their contact information so payment can be mailed]

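### Only self-reported letter readers see a pro-counseling statement in the block directly before the counseling questions, so the planned-behavior answers may lean in the letter's favor

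*Protocol*

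**What the plan says.** Section 6.8 presents the online format as the remedy for order effects: "Online administration allows for additional randomization of response options, offsetting potential order effects". Section 6.10 gives the purpose as positional bias: "Lists of response options will be randomized to minimize the potential for positional bias". Section 6.10 also disables the back button, so that "once a question is submitted, HCPs do not have the option of revisiting it".

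One rule in Section 6.8 governs order between questions: "Questions pertaining to reading and reactions to the DHCP letter are asked after the risk questions". It does not mention the counseling items.

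In Appendix II, only the six Q15 statements and the Q17 options carry a randomization note. Questions Q15 to Q22 run in numbered order. Q18 asks whether the respondent read the letter. A Yes leads to Q19a to Q19d; No or not recalling leads past Q19 to Q20. Q19a opens "The discussion of prescribing information encouraged me to better counsel my patients about the use of" and goes on to name the product.

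Q20 asks about current counseling practice, Q21 about the need for counseling and Q22 about the intention to counsel. Section 6.7.5 says planned behavior is addressed by two questions, need and intention, which are Q21 and Q22. Section 6.9 says the sponsor will explore whether prescribers show acceptable understanding and suitable behavior without having read the letter.

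**The concern.** The protocol recognizes that letter items can color later answers, because it keeps them behind the risk questions. It does not apply the same reasoning to the counseling questions, which follow the letter-reaction block directly.

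The skip rule makes this more than ordinary carry-over. A cue shown to everyone could raise the overall level of an answer. A cue shown only to self-reported readers can also create a difference between readers and non-readers. At Q21 and Q22 that difference would look like an effect of the letter when part of it comes from the questionnaire. The planned-behavior results and the Section 6.9 exploration are what is at stake.

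**Working it through.** **Who sees what before the counseling endpoints (Appendix II).**

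| Item | Yes at Q18 | No or not recalled at Q18 |
|---|---|---|
| Q15 to Q17 | shown | shown |
| Q18 (read the letter?) | shown | shown |
| Q19a (letter encouraged better counseling) | shown | skipped |
| Q19b to Q19d | shown | skipped |
| Q20 (counseling practice) | shown | shown |
| Q21, Q22 (planned-behavior endpoints) | shown | shown |

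The two paths differ only in the Q19 block, which sits immediately before Q20.

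**Do the stated safeguards reach this?**

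- Shuffling response options acts within a question and cannot change which question comes first.
- Shuffling the Q15 statements leaves Q15 as a block ahead of Q16 and does not touch Q19 to Q22.
- The disabled back button prevents revision of earlier answers. It does not stop an earlier item from influencing a later one.
- The Section 6.8 ordering rule shields Q15 and Q16 from Q18 and Q19, but not Q20 to Q22.
- Section 6.9 does not list carry-over between questions as a limitation.

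**Size, by assumption only.** The documents give no figure for carry-over. The plan's precision serves as a yardstick. Section 6.5 states ±5.49 points for n = 200, p = 80% and N = 10,000:

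1.96 × √(0.8 × 0.2 / 200) × √(9,800 / 9,999) = 0.0549, which reproduces ±5.49. At p = 70% the same formula gives ±6.29, also as in Table 1.

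Let p be the true share giving the pro-counseling answer, equal in both groups. Let c be the assumed share of the remaining readers whom Q19a moves to that answer, beyond any effect of items everyone sees. The spurious gap between readers and non-readers is (1 − p) × c:

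| p | c = 10% | c = 20% | c = 30% |
|---|---|---|---|
| 70% | 3.0 points | 6.0 points | 9.0 points |
| 80% | 2.0 points | 4.0 points | 6.0 points |

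If a share r of respondents are readers, the overall percentage rises by r × (1 − p) × c. At c = 20% and r = 50%, 70% and 90%, this is 3.0, 4.2 and 5.4 points for p = 70%, and 2.0, 2.8 and 3.6 points for p = 80%. These compare with half-widths of 6.29 and 5.49.

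The subgroup comparison is itself imprecise. With r = 70% (140 readers, 60 non-readers) and p = 80%, the 95% margin on the difference, ignoring the finite population correction, is 1.96 × √(0.16/140 + 0.16/60) = 0.121, or about 12 points. A gap of this origin would usually lie within sampling error, but it is systematic and a larger sample would not remove it.

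**The case against.** The strongest defense has three parts.

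- The effectiveness rule in Sections 6.4 and 6.7.4 rests on the key safety statements, all asked before Q19. The counseling items are secondary and descriptive, and no formal comparison by reading status is specified. This stands, and it limits what is at risk.
- The cue is weak. Q19a is an agree/disagree item that respondents may reject, three further statements follow it, Q20 raises counseling with everyone, and one Q21 option tells everyone that prescribers should counsel. This shared exposure may dilute the cue. It does not equalize it, since Q19 still precedes Q20 for readers only.
- Sections 6.8 and 6.10 can be read as addressing only the order of options, and Section 6.8 does contain one between-question control. That is fair. The point is that this control stops short of the counseling questions.

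A reader might infer two stronger criticisms that the documents do not support.

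One is that Q15e gives away Q16. Q15e opens "It is important to instruct your patients that they should always have" and refers to a backup pen. The next question asks "In the event of a Humulin® R U-500 KwikPen® malfunction, what would you instruct patients to do" and lists using a backup pen as a keyed option. But Q16 shows that option to everyone anyway, it is one of three keyed options, and Q15e says nothing about the two contact options or the unsafe syringe option.

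The other is that answers are revealed during the survey, because Section 6.10 says "Correct responses will be provided to the physicians following recording of their response, allowing for feedback on performance". Section 6.2 and Appendix III describe links sent with a thank-you email, and no programming note in Appendix II calls for feedback within the survey. The sentence is compatible with emailed answers.

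**Conclusion.** The question order exposes self-reported readers, and nobody else, to a pro-counseling statement directly before the counseling questions. This may bias Q21 and Q22, and the Section 6.9 look at behavior among non-readers, in the letter's favor. Option randomization does not address it.

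The exposure pattern follows directly from the Q18 skip. That Q19a shifts answers, and in which direction, is a plausible expectation the documents do not demonstrate. The 2 to 9 point gap rests wholly on an assumed 10 to 30% response to the cue and equal true rates of 70 to 80%. The primary effectiveness conclusion is unaffected. The change is worth making because it is easy and removes a difference in exposure that analysis could not separate from having read the letter.

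**What to change.** In Appendix II, keep Q15 to Q17 where they are, ask Q20 to Q22 next, and ask Q18 and Q19 last. Change the Q18 skip so that respondents answering No or not recalling go to the closing screen. Keeping Q17 in place leaves it close to the true/false statements it refers to.

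In Section 6.8, extend the ordering sentence to say that letter-reading and reaction items come after both the risk questions and the counseling questions.

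The cost is re-sequencing the online form and editing one sentence, ideally before user acceptance testing. The small downside is that counseling answers may carry over into Q19a, but everyone who sees Q19a will then have answered the same counseling questions first. Re-ordering does not make the reader/non-reader comparison causal, since readers are self-selected.

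Optionally, reword the Section 6.10 feedback sentence to say that correct answers are emailed after the survey, in line with Section 6.2 and Appendix III.

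Moving Q16 ahead of Q15 is not recommended. It would show the backup-pen option before Q15e, which is also a primary endpoint, and so only relocate the cue.

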6.2.1 Population

The initial population in scope for selection consists of the 15,179 HCPs who were sent a DHCP letter and prescribe the Humulin[®] R U-500 KwikPen[®] within 12 months of the launch date. The sampling frame is limited to the 10,442 HCPs (69%) who have a valid email, as recruitment will be implemented via email only.

Initially 1,000 HCPs will be randomly selected in order to obtain 200 completed surveys with a target response rate of 20%. The response rate will be monitored throughout the data collection period of 3-5 months. Of the 1000 initially sent, if any are undeliverable, they will be replaced.

Follow-up via phone or email or randomly selecting additional HCPs will be assessed as options to obtain 200 completed surveys if the initial response rate is lower than 20%. If the response rate is higher than 20% then no follow-up or additional HCP sample will be required.

HCPs who complete the screener and qualify for the survey are included in the survey's analysis population. Data collected on the screener and on the survey will be available for this analysis population.

HCPs who complete the screener, but do not qualify to participate in the survey are included in the screen failures analysis. These HCPs may fail the screener because they indicate that they have not met one of the inclusion/exclusion criteria. Data collected on the screener will be available for this population.

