6.4 Data Sources

Responses to the HCP Survey comprised of closed-ended questions or statements with multiple response choices (i.e., questions or statements asking the HCPs to choose from a defined list of responses) and HCP information contained in the sampling frame are the source of the study data.

Screening questions:

- Prescribed Humulin® R U-500 KwikPen® product
- Aware of having received DHCP letter
- HCPs or their immediate family members are not current or past employees of Lilly, Covance, SA, or the FDA
- Didn't previously participate in the survey
- Agree to participate

Data on demographic characteristics:

- Age group
- Gender
- Role at facility
- Facility type
- State or territory of practice
- HCP medical specialty (e.g., General Internal Medicine, Endocrinology/Diabetology, Family Medicine, and Other)

- Number of years practicing medicine/nursing (e.g., <5 years, 5-10 years, 11-15 years, and >15 years)
- Number of Humulin[®] R U-500 KwikPen[®]-treated patients the HCPs prescribed to or managed in the 12 month period preceding the survey (self-reported). Response options are categorical in nature, e.g., 1-5 patients, 6-10 patients, 11-20 patients, and >20 patients.

Data pertaining to evaluation of the effectiveness of the risk minimization measures:

The survey includes questions/statements that will assess HCP understanding about the risks and associated behavior of the HCPs to minimize these risks. The understanding level and behaviors will be analyzed using descriptive statistics and confidence intervals (CIs) and will be used to determine the effectiveness of the risk minimization measures:

- Awareness of the DHCP letter on the correct use of Humulin[®] R U-500 KwikPen[®]
- Understanding of the key safety messages
- Self-reported practices and intentions with respect to communication of the key safety messages in clinical practice

The RMiP will be considered effective if the majority of HCPs demonstrate they are aware of the key safety messages communicated for Humulin[®] R U-500 KwikPen[®].

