6.9 Limitations of the Research Methods

The sample is subject to volunteer bias because HCPs decide independently whether or not to respond to the invitation to participate. There is no active follow-up to the recruitment invitation planned. To moderate the impact of self-selection, HCPs will be randomly selected from the list of HCPs who received the DHCP letter, which should be generalizable to the overall HCP population who are educated about the use of Humulin[®] R U-500 KwikPen[®].

Additionally, the participation in the survey is reliant on the HCP's recall of whether or not the DHCP letter was received. However, it is possible that HCPs may simply not recall receiving the materials that were, in fact, received. It is also possible that they have acceptable understanding of the risks and appropriate behaviors despite not having read the DHCP letter. Lilly will explore the latter possibility with variables described in Section 6.3.

As with most survey data, information is self-reported and therefore susceptible to reporting biases. There may ultimately be discrepancies between what HCPs report about their intentions and what they ultimately do.

Lastly, this survey is administered only online. While the majority (69%) of the HCPs on the sampling frame (see Section 6.2.1) provided an email address, not everyone on the list has an email address listed. This could introduce additional selection bias.

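### Section 6.8 credits random sampling with helping to avoid volunteer bias, which it cannot do and which 6.9 contradicts; the comparison described in 6.8 cannot show non-response bias

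*Protocol*

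**What the plan says.** Section 6.8 (Quality Control) lists the sampling method among its data-quality strategies and says that it "helps ensure representativeness, avoid volunteer bias, and provides an additional means for ensuring valid data". The next sentence says that in the analysis "demographic criteria are summarized for those who met survey inclusion criteria against those who did not meet the criteria".

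Section 6.9 (Limitations) says: "The sample is subject to volunteer bias because HCPs decide independently whether or not to respond to the invitation to participate". It then presents random selection from the list of letter recipients as a way to moderate self-selection, and says the result should generalize. It also says: "There is no active follow-up to the recruitment invitation planned". Section 6.2.1 keeps follow-up open if response falls below 20%: "Follow-up via phone or email or randomly selecting additional HCPs will be assessed as options to obtain 200 completed surveys".

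On data, Section 6.4 states that survey responses and "HCP information contained in the sampling frame are the source of the study data". Section 6.7.2 plans counts of invitations by specialty (the line seems to have lost a word), responders, ineligible HCPs with reasons, eligible HCPs and completers. Section 6.7.3 summarizes demographics for the Analysis Set, the Screening Set and a group called all HCPs, which is not defined.

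**The concern.** Sections 6.8 and 6.9 describe the same property of the design in opposite ways, and 6.8 is the one that is wrong. A random draw makes the invited sample representative of the list it was drawn from. Volunteer bias arises afterwards, when each invited HCP decides whether to respond, and the draw has no influence on that decision.

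The comparison in 6.8 does not fill the gap. To be classed as meeting or not meeting the criteria, an HCP must have opened the invitation and answered the screener, and Section 6.7.1 also leaves immediate refusals out of the Screening Set. Non-responders are in neither group.

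Each primary endpoint is a single proportion among completers, with no comparator, and Section 6.7.4 calls the risk minimization plan effective if a majority of HCPs answer correctly. If the HCPs who respond are the better informed ones, which is plausible but not documented, the proportions are too high, and the stated confidence interval does not reflect this.

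**Working it through.** **Inputs**
- Target: 200 completed surveys from 1,000 invitations, 20% (6.2.1).
- Planning value: 80% correct, n = 200, half-width ±5.49 points; Table 1 assumes N = 10,000 (6.5).
- Criterion: a majority answering correctly (6.7.4).
- Assumed, because the protocol gives no figure: the share *e* of invitees who are eligible, and the gap in percent correct between responders and non-responders.

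**The plan's own figure.** 1.96 × √(0.8 × 0.2 / 200) × √((10,000 − 200) / 9,999) = 0.05544 × 0.9900 = 0.0549, that is ±5.49 points. It reproduces. It covers sampling error only.

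**Who is in each group**

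| Group | Section | Includes non-responders? |
|---|---|---|
| Met inclusion criteria | 6.8, 6.7.1 | No |
| Did not meet criteria (Screening Set) | 6.8, 6.7.1 | No; immediate refusals also left out |
| All HCPs | 6.7.3 | Undefined |
| Invitations issued, by specialty | 6.7.2 | Yes, as counts |

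Even if all HCPs means all invitees, age, gender, years in practice and number of patients treated are collected in the screener (Appendix II). They do not exist for HCPs who never opened it. Only variables held in the sampling frame can describe non-responders. Specialty is the one that 6.7.2 implies is available for every invitee.

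**Size.** Bias of the completer proportion = non-response fraction among eligible HCPs × gap. With 1,000*e* eligible invitees and 200 completers, the fraction is 1 − 200/(1,000*e*) = 1 − 0.2/*e*.

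| Assumed *e* | Non-response fraction | Bias at a 10-point gap | Gap giving 5.49 points of bias | Gap needed to bring 80% down to 50% |
|---|---|---|---|---|
| 100% | 80% | 8.0 | 5.49/0.80 = 6.9 | 30/0.80 = 37.5 |
| 60% | 67% | 6.7 | 5.49/0.667 = 8.2 | 30/0.667 = 45 |
| 40% | 50% | 5.0 | 5.49/0.50 = 11.0 | 30/0.50 = 60 |

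For an item that only 60% of completers answer correctly, the last column becomes 10/0.80 = 12.5, 10/0.667 = 15 and 10/0.50 = 20 points.

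**Fallback sampling.** If response is low, drawing more HCPs at random (6.2.1) restores the count of 200 but not the response rate. At an assumed 10% response with all invitees eligible, the fraction rises to 90%.

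**The case against.** The strongest reply is that 6.8 says only that sampling helps, and that 6.9 is open about the bias. Compared with open recruitment, a random draw from a list does limit who can put themselves forward. The eligible-versus-ineligible summary stands in its own sentence, is never called a non-response check, and has a use of its own: it shows who is lost at screening, including HCPs who do not recall the letter.

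Much of this stands. The protocol conceals nothing, and the screening summary should stay. But helping still implies some effect on the decision to respond, and there is none among those invited.

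Several stronger readings are tempting, and the documents do not support them:
- *That the plan could not reveal non-response bias at all.* The counts in 6.7.2, the frame data in 6.4 and the all-HCPs group in 6.7.3 would support a limited check on specialty. It is just not stated.
- *That 80% of invitees contribute nothing.* Some of the other 800 will be screen failures, who supply screener data and are outside the target population. So 80% is an upper bound on eligible non-response.
- *That the effectiveness verdict is in doubt.* At 80% correct, a 10-point gap leaves at least 72%; losing the majority needs a gap above 37.5 points even at the upper bound.
- *That the HCPs without e-mail are an undisclosed gap.* Section 6.2.1 says "The sampling frame is limited to the 10,442 HCPs (69%) who have a valid email". The other 4,737 of 15,179 (31.2%) are therefore visible, and 6.9 names the possible selection bias.

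**Conclusion.** The point holds as a wrong statement in 6.8, in conflict with 6.9, together with a described comparison that cannot speak to non-response. The wording error and the composition of the compared groups follow from the protocol's text and need no assumption.

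The size does rest on assumptions. With a 10-point gap and an eligible share between 40% and 100%, the bias is about 5 to 8 points, comparable to ±5.49. Neither the gap nor its direction is documented. It matters for how far the reported percentages can be taken to describe all invited prescribers. It does not overturn a majority verdict at the planning value; an item near 60% correct would be more exposed.

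**What to change.** 1. In 6.8, delete the claim about volunteer bias. In 6.9, replace the claim that random selection moderates self-selection: it makes the invited sample representative of the e-mail frame but does not reduce self-selection among those invited. While editing, align the follow-up statements in 6.9 and 6.2.1.
2. Keep the eligible-versus-ineligible table and add one that sets completers, and all screener responders, against all invited HCPs on specialty and any other variable the frame holds. Define the all-HCPs group in 6.7.3.
3. Optionally, report the primary proportions post-stratified to the specialty distribution of the invited sample or the frame, labelled as a sensitivity analysis. State that it removes only bias related to specialty, and that the frame includes HCPs who would fail screening. The weighting details can sit in the SAP.

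The cost is a few sentences and one table, with no new data collection for specialty. The protocol does not show which other variables the frame holds, so anything further depends on that. The optional estimate loses a little precision.
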